### Materials and Methods

The scientific review committee and the committee for the protection of human participants of the local university (protocol number 1.376.881) approved this clinical investigation. It was registered in the clinical trials gov registry under the identification number NCT02956070. We performed this study using the protocol that the Consolidated Standards of Reporting Trials (CONSORT) statement established. Based on pre-established criteria, we selected 70 volunteers for this study. The study was performed from February 15, 2016, to July 12, 2016.

Two weeks before the bleaching procedures, each volunteer received a dental prophylaxis with pumice and water in a rubber cup and signed an informed consent form.

Study design: This was a randomized, triple-blinded, parallel-group clinical trial in which the volunteer, operator, and evaluator were blinded to the group assignment. A third researcher, not involved in the evaluation process, was responsible for the administration of the drugs. The study was carried out in the clinics of the School of Dentistry of Fluminense Federal University (Nova Friburgo, RJ, Brazil). Patients were recruited as they seek for treatment in the clinics of Dentistry of both Universities. No advertisement was made for participant recruitment. Patients were recruited in the order in which they reported for the screening session, thus forming a sample of convenience.

Inclusion and exclusion criteria: Volunteers included in this clinical trial were at least 18 years old, had good general and oral health, and did not report any type of TS. The volunteers were required to have 8 caries-free maxillary anterior teeth without restorations, be free of periodontal disease and review and sign the informed consent form. The central incisors had to be shade A1 or darker as judged by comparison with a value-oriented shade guide (VITA Classical, VITA Zahnfabrik). Despite the fact that the color shade A1 is one of the lightest colors measurable using VITA Classical, many volunteers with A1 shade teeth seek dental bleaching, as they are dissatisfied with the color of their teeth.

Two calibrated investigators ([name]) independently performed the color evaluations with the shade guide. The 2 examiners, blinded to the allocation assignment, schedule the volunteers for bleaching and evaluated their teeth against the shade guide at baseline and 1 week after the procedure. The 2 examiners were required to have an agreement of at least 85% (Kappa statistic test) before beginning the study evaluation.

Volunteers with anterior restorations or dental prostheses, with anterior orthodontic apparatuses or with severe internal tooth discoloration (tetracycline stains, fluorosis, pulpless teeth) were not included in the study. In addition, pregnant and lactating women, participants with any other pathology that could cause sensitivity (such as gingival recession, dentinal exposure, visible cracks in teeth), those taking anti-inflammatory or analgesic drugs, those who smoked or volunteers who had undergone tooth-whitening procedures were excluded. Those who reported past or present health problems in the stomach, heart, kidneys or liver; those who reported the continuous use of anti-

inflammatory or analgesic drugs; those patients with diabetes, hypertension or the use of antihypertensive drugs; or patients who reported allergies to dexamethasone and lactose were also excluded from the study.

Sample size calculation: The primary outcome of this study was the absolute risk of TS. The absolute risk of TS (that is, the number of patients [percent] who reported pain at some point during dental bleaching) was reported to be approximately 90% for a similar 35% hydrogen peroxide bleaching product [20,21,36]. Thus, a minimum sample size of 70 participants was required to have a 90% chance of detecting, as significant at the 2-sided 5% level, a decrease in the primary outcome measure from 90% in the control group to 60% in the experimental group.

Random sequence generation and allocation concealment: The authors used blocked randomization (block sizes of 2 and 4) with an equal allocation ration, using a 3rd-party service (Sealed Envelope), which did not intervene in the study. Opaque and sealed envelopes containing the identification of the groups were prepared.

Study intervention: We divided volunteers into the dexamethasone group, who received the anti-inflammatory (dexamethasone, capsule – 8 mg) and application of a placebo gel, and the control group, who received placebo capsules and the application of desensitizing gel containing 6% potassium nitrate and 0.10% fluoride sodium (Soothe, SDI, Victoria, Australia). All volunteers received the same bleaching treatment, which 4 experienced operators ([name]) performed. One week before the in-office bleaching session, volunteers received individual pots containing 6 capsules in total, with the dexamethasone (Handled by Bem Viver laboratory Ltda), or placebo, in identical capsules depending on their allocation group, which contained the same components of the dexamethasone drug except for the active ingredient (Table 1).

The control group received placebo capsules and the application of desensitizing gel containing 6% potassium nitrate and 0.10% fluoride sodium, and the dexamethasone group received the anti-inflammatory (dexamethasone, capsule - 8mg) and application of a placebo gel. Volunteers were treated in 2 clinical sessions with an interval of 7 days (one week) between them. The protocol for use of the product was as follows: The volunteers in the experimental group received 6 capsules of dexamethasone 8 mg each, which was administered orally, initially 2 days before the 1st bleaching query (8mg, 9 AM, 2 days before the bleaching session; 8mg, 9 AM, 1 day before the bleaching session; 8mg, 9 AM, on the day of the bleaching session) [40]. This same scheme was performed for the 2nd bleaching session, which was 7 days after the 1st. The operators instructed the volunteers to increase adherence to the protocol, and the researches made telephone calls and sent cell phone text messages to remind the volunteers of every capsule to be taken.

Before the dental bleaching, gingival tissue was isolated from teeth using a light-cured resin (Gingival Barrier, SDI), and each tooth was light-cured for 10 seconds using a light curing unit with 1200 mW/cm2 light intensity (Radii-cal, SDI). After the placement of a lip retractor (OptraGate – Ivoclar Vivadent), the operator used the 37.5% hydrogen peroxide gel (polaoffice+, SDI) in three 8-

minute applications for both groups in accordance with the manufacturer's directions. The bleaching agent was refreshed every 8 minutes during the 24-minute application period. At the end of each session, a single researcher responsible for the blinding [name] delivered a single syringe to the operator, which would contain desensitizing gel if the patient was in the control group, or placebo gel containing only carbopol (no active ingredient) if the patient was in the dexamethasone group. The gel was applied with a brush on the labial surface of the whitened teeth for 2 to 3 minutes as the manufacturer (Soothe SDI Dental Limited) directed. Two bleaching sessions were performed 1 week apart.

TS evaluation: TS was evaluated during bleaching and up to 1 hour, 24 hours and 48 hours postbleaching. The volunteer was asked to indicate the numeric value of the degree of sensitivity for each of the periods above, using a 5-point numeric rating scale (NRS) in which 0= none, 1= mild, 2= moderate, 3= considerable and 4= severe [2,4,5,7,23].

In addition, the volunteers were also instructed to record the pain intensity using the visual analogic scale (VAS) [3,6-9]. This scale is a 100-milimeter horizontal line with scores of 0 and 100 at their ends, in which 0 = no sensitivity and 100 = severe sensitivity. The volunteer had to mark with a vertical line across the horizontal line of the scale the intensity of the TS. Then, the distance in millimeters from the zero ends was measured with the aid of a millimeter ruler.

The data from each bleaching session were evaluated separately and were merged. For this purpose, the worst score or numeric value obtained in both bleaching sessions was considered for statistical purposes and the determination of the overall risk and intensity of TS.

If the volunteer scored 0 (no sensitivity) in all time assessments from both bleaching sessions, this volunteer was considered to be insensitive to the bleaching protocol. In all other circumstances, the volunteers were considered to have sensitivity stemming from the bleaching procedure. This dichotomization allowed us to calculate the absolute risk of TS, which represented the percentage of volunteers who reported TS at least once during treatment. We also calculated the overall TS intensity.

Color evaluation: Shade evaluation was performed before 1 week after the 1st bleaching session, but before the 2nd session, and 1 week after the 2nd bleaching session. Color evaluation was not performed immediately after each bleaching session so that the effect of dehydration and demineralization on color measures could be avoided. We performed the color evaluation using the shade guides of VITA Classical and the VITA Bleachedguide 3D-MASTER. (VITA Zahnfabrik).

For the color evaluation, the VITA Classical shade guide's 16 tabs were arranged from highest (B1) to lowest (C4) value. Although this scale is not linear in the truest sense, we treated the changes as representing a continuous and approximately linear ranking for the purpose of analysis, as already performed in several published studies [2,3,5,8,9,15,23,25]. The VITA Bleachedguide 3D-MASTER contains lighter shade tabs and is already organized from the highest (0M1) to lowest (5M3) value [24]. The measurement area of interest for shade matching was the middle 1/3 of the facial surface of the central incisor, according to the American Dental Association guidelines [4,12,15].

The 2 examiners, masked to the allocation assignment, scheduled the volunteers for bleaching and evaluated their teeth against the shade guide at the different time assessments. Color changes were calculated from the beginning of the active phase up to and including recall times by calculating the change in the number of shade guide units ( $\Delta$ SGU), which occurred toward the lighter end of the value-oriented list of shade tabs. In the event of disagreements between the examiners during shade evaluation, a consensus was reached through discussion.

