PRODUCT	INGREDIENTS
Pola Office + SDI*	• 37.5% hydrogen peroxide
	
 
potassium nitrate
 

Soothe SDI*	• potassium nitrate 6.0%
	• fluoride ions 0.10%
	• water 89.60%
	• thickener 4.20%
	• sodium benzoate 0.10%
Dexamethasone capsules**	
 
dexamethasone base 8mg
 

•	• starch 50%
	
 
lactose monohydrate 35%
 

	
 
dibasic calcium phosphate 14%
 

	• magnesium stearate 1%
Placebo capsules**	• starch 50%
	
 
lactose monohydrate 35%
 

	
 
dibasic calcium phosphate 14%
 

	• magnesium stearate 1%
Placebo gel**	• carbopol

\* SDI, Victoria, Australia

\*\* Handled by Bem Viver laboratory Ltda, registration number 09047030/0001-28, located at [name]. Batch of the product: 189155.

# TABLE 2

Participants who exp	erienced too	th sensitivity d	uring the bleaching regi	men in the control group	
and dexamethasone g	group*				
TREATMENT	TOOTH SENSITIVITY (N°. OF PARTICIPANTS)		ABSOLUTE RISK	RISK RATIO (95% CONFIDENCE	
	Yes	No		INTERVAL)	
Control	33	2	0.94	0.24 (0.05 1.26)	
Dexamethasone	28	7	0.80	0.24 (0.05 – 1.26)	
* Fischer's exact test	(p=0.075).				

TABLE 3

Medians and interquartile (1 and 3 interquartile) ranges of the tooth sensitivity at different assessment points using the numeric rating scale (NRS).

ACCECCMENT		First Session		Second Session			
ASSESSMENT TIMES	Control	Dexamethason e	Compariso n group	Control	Dexamethason e	Comparison group	
During bleaching	$0(0-1)^{A}$	0 (0-1) A	NS †	0 (0-1) A	0 (0-1) A	NS	
Up to 1h after bleaching	0 (0-1) A	0 (0-1) A	NS	0 (0-1) A	1 (0-1) A	NS	
Up to 24h after bleaching	0 (0-1) A	0 (0-1) A	NS	0 (0-2) A	0 (0-1) A	NS	
Up to 48h after bleaching	0 (0-0) B	0 (0-0) B	NS	0 (0-0) B	0 (0-0) B	NS	

\* Within each column, significant differences are represented by different uppercase letters.

† NS: No significant difference between groups.

TABLE 4

 $Means \ (standard \ deviations) \ of \ the \ tooth \ sensitivity \ intensity \ at \ the \ different \ assessment \ points \ using \ visual \ analog \ scales.*$ 

A COLECCI MENTE	First Session			Second Session		
ASSESSMENT TIMES	Control	Dexamethasone	Compariso n group	Control	Dexamethason e	Comparison group

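### Sample size: the stated 90% power is about 78% under the planned Fisher test at the plan's own rates, and the 90% control risk is not shown to apply to an active-gel control arm

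*Combined protocol and SAP*

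**What the plan says.** In Materials and Methods, under Sample size calculation, the primary outcome is the absolute risk of tooth sensitivity, which "was reported to be approximately 90% for a similar 35% hydrogen peroxide bleaching product". The paragraph then sets 70 participants as the least number that gives 90% power with a two-sided 5% test. The difference to be detected is "a decrease in the primary outcome measure from 90% in the control group to 60% in the experimental group". The paragraph mentions no desensitizer and gives no source for the 60%.

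Under Study intervention, the comparator is "the control group, who received placebo capsules and the application of desensitizing gel containing 6% potassium nitrate and 0.10% fluoride sodium". The dexamethasone arm gets active capsules and a placebo gel. Both arms are bleached with a 37.5% peroxide product. Under the paragraph on TS evaluation and the text just before it, the gel is applied at the end of each of the two sessions, and a participant counts as sensitive after any non-zero score at any assessment in either session.

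Table 1 lists "potassium nitrate 6.0" percent for the desensitizing gel. It also lists potassium nitrate, with no percentage, among the ingredients of the bleach that both arms receive.

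Statistical analysis names Fisher's exact test at 0.05 for the absolute risk. The Results report no significant difference and read the relative risk and its interval as evidence that the drug protocol did not reduce sensitivity.

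**The concern.** The primary result was not significant, so readers will rely on the stated power and on the description of what was compared. Both need correction.

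- **Power.** If 70 participants do not give 90% power at 90% versus 60%, the trial was less able to detect its planned difference than it says, whatever the comparator.
- **Control risk.** The 90% is quoted for a bleaching product and then used, without comment, for an arm that also receives an active gel. No text adjusts it, says the cited reports used such a gel, or argues that the rate carries over. Power at this sample size is sensitive to that input.
- **Interpretation.** A statement that the drug protocol had no effect can be read as a comparison with nothing. The trial compared dexamethasone plus placebo gel with placebo capsules plus an active gel.

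**Working it through.** **Inputs.** Control risk p1 = 0.90, experimental risk p2 = 0.60, two-sided alpha 0.05, power 0.90 and total N = 70 come from Sample size calculation. Equal allocation (the randomization paragraph) gives n = 35 per arm. Fisher's exact test comes from Statistical analysis. The observed control count of 33/35 comes from Table 2.

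**Step 1: can the plan's 70 be reproduced?** Pooled normal formula, with mean risk p̄ = 0.75:

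n = [z(0.975)·√(2·p̄·(1−p̄)) + z(0.90)·√(p1(1−p1) + p2(1−p2))]² / (p1−p2)²

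= [1.960·√0.375 + 1.282·√0.33]² / 0.09 = (1.200 + 0.736)² / 0.09 ≈ 41.7, so 42 per arm and 84 in total.

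Other standard formulas give totals of 78 (unpooled), 80 (arcsine) and 98 (continuity-corrected). None gives 70. Totals near 70 appear only when a stated input is changed: one-sided 5% at 90% power gives 68 (pooled), and two-sided 5% at 85% power gives 72 (pooled).

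**Step 2: power at 35 per arm, 90% versus 60%.**

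Pooled normal: Φ{[0.30·√35 − 1.960·√0.375] / √0.33} = Φ{(1.775 − 1.200) / 0.574} = Φ(1.00) = 84%. The unpooled version gives 87%.

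Two-sided Fisher, by exact enumeration: sum Bin(a; 35, p1) × Bin(b; 35, p2) over all 36 × 36 outcomes (a, b) with Fisher p ≤ 0.05. The result is 0.785, or 78%. The shortfall against the stated figure is 90 − 78 = 12 points, with no gel effect assumed.

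**Step 3: sensitivity to the control risk.** Same enumeration, with the experimental risk held at 60%. It is held fixed because the dexamethasone arm gets placebo gel, so a gel effect would not lower its risk.

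| Control risk | Status | Fisher power |
|---|---|---|
| 94.3% | observed, 33/35 | 93% |
| 90% | planning value | 78% |
| 85% | assumption | 56% |
| 80% | assumption | 36% |

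Moving from 90% to 85% costs 0.785 − 0.565 = 0.220, or 22 points. The documents give no planning rate under gel, so 85% and 80% only show the range.

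**Step 4: the in-trial check.** 33/35 = 94%, with an exact (Clopper-Pearson) 95% interval of 81% to 99%. Against 60%, Fisher power is about 40% at the lower limit and over 99% at the upper limit.

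**The case against.** A reader might infer that the 90% belongs to a different comparator. The documents do not support that. The paragraph does not say whether the cited reports used a desensitizer, and those reports are not available here. The most that can be said is that the rate is not shown to apply.

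A reader might also infer that if the gel works at all, the control risk must be below 90%. That does not follow. The outcome is ever/never and counts pain during the first bleaching, while the gel is applied only at the end of each session. It cannot prevent that first pain, and it could reduce intensity or duration without changing who is counted as sensitive. It could still prevent later first episodes, so the question stays open.

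The strongest evidence on the other side is the observed control risk under gel of 94%, above the planning value. In hindsight 90% does not look too high, although an observed rate does not supply a justification that was absent at planning.

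The potassium nitrate in the bleach and the 37.5% versus 35% strength add little. Both arms share the bleach, the text openly calls the cited product similar, and the documents never describe the contrast as desensitizer versus none.

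Finally, a completed trial is best read from its confidence interval, and both regimens are described in full under Study intervention. That limits how much a power table can say about the result. It does not touch Step 2: 78% against a stated 90% holds whatever view is taken of the gel.

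**Conclusion.** The point holds in two parts. The first is firm and uses only the plan's own inputs: 35 per arm at 90% versus 60% gives 78% power by the planned two-sided Fisher test (84% by pooled normal approximation), not 90%. The second is a gap in justification: the 90% control risk is quoted for a bleaching product, and nothing shows that it applies to a control arm given an active gel. Its direction and size are unknown. Under assumed control risks of 85% and 80% power would be 56% and 36%; at the observed 94.3% it would be 93%. All of these assume an experimental risk of 60%, which is itself unsourced. The observed rate gives no sign that the planning value was too high, so the documents do not support saying that the trial used the wrong control rate.

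**What to change.** - **Stated power.** In Sample size calculation, replace the 90% chance of detection with 78% (two-sided Fisher, 35 per arm, 90% versus 60%).
- **Source of the 90%.** Say that it is a rate reported for a 35% peroxide bleaching product and is not shown to apply under an active gel. If the cited reports did use a comparable gel, one sentence saying so settles this part.
- **Sensitivity.** Add the short Fisher table against 60%: 94.3% gives 93%, 85% gives 56%, 80% gives 36%. Label 85% and 80% as assumptions. Put the observed control risk of 94% (81% to 99%) beside it as no sign that 90% was too high.
- **Results wording.** Replace the statement that the drug protocol had no effect with one that no significant difference was shown between dexamethasone plus placebo gel and placebo capsules plus potassium nitrate/fluoride gel.

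The cost is rewording in two places and one small table. No new data or participants are needed. The downside is a less favourable stated power.

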## Statistical analysis

We performed the analysis after the intention-to-treat protocol, and we involved all participants who were randomly assigned [21]. In cases of missing data, the last observation was carried forward. The statistician was masked to the study groups. The absolute risk of TS and its intensity were evaluated by using Fischer's exact test. ( $\alpha = 0.05$ ). The authors calculated the relative risk as the confidence interval for the effect size.

Comparison of the TS intensity (NRS data) of the 2 groups at the 2 different assessment points were performed by using the Mann-Whitney U test, and comparisons between times within each group were performed using the Friedman test. The comparisons of the TS intensity obtained with the VAS scale were evaluated by using a 2-way repeated measures ANOVA and Tukey's test.

Color changes between groups ( $\Delta$ SGU between base line versus 1 week after the 2nd bleaching session) were compared by using a t test, and the shade changes were evaluated by using Student's t test. In all statistical tests, the significance level was 0.05. We performed all analyses by using the software SPSS for windows version 20.0 (IBM).

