#### Results

We screened 123 participants examined in the dental chair to check if they met the inclusion and exclusion criteria (Figure 1). The bleaching procedures were implemented exactly as planned and no modification was performed.

Characteristics of included participants: The baseline color of the volunteers was similar (control group: 5.9 [1.9]; dexamethasone: 5.6 [2.1]); the mean age (SD) between volunteers was similar between the groups (control: 22.5 [2.1] and dexamethasone: 22.3 [2.7]), ranging from 19 to 29 years. Thirty-four percent of the volunteers from the control group, and 23% of the volunteers from the dexamethasone group were men.

*Protocol adherence and dropouts*: No discontinuity in both treatment groups was found in the clinical investigation. All volunteers attended the recall visit 1 week postbleaching.

*Tooth Sensitivity*: Two volunteers, 1 from each group, took an analgesic to alleviate the bleaching-induced TS (Tylenol, Janssen Cilag Farmacêutica) in the period from 5 to 7 hours after the 2nd and last clinical bleachings.

Table 2 shows the number of participants who experienced TS during the bleaching regimen in the control group and dexamethasone group. In this table, it is shown that no significant difference was observed between groups (p = 0.075). The relative risk, along with the 95% confidence interval, is also evidence that the use of the experimental drug protocol had no effect on the reduction of TS.

Tables 3 and 4 show that the TS was similar in both groups, at different assessment points, in both sessions, using both pain scales. It is also seen that the bleaching-induced TS did not last longer than 48 hours after the bleaching protocol (Tables 3 and 4).

Color Evaluation: Significant whitening was observed in both groups (P < .001). The descriptive data from bleaching obtained after the 1st and 2nd bleaching sessions can be seen in Table 5. At the end of the bleaching protocol, a whitening of approximately 3 shade guide units was detected for both groups.

The results of the subjective shade evaluation (VITA Classical: P = 0.27; VITA Bleachedguide 3D-MASTER: P = 0.68) matched the hypothesis of equality between the groups after bleaching. The effect size and the confidence interval for the overall mean difference is also shown in Table 5 and is evidence of no statistical difference between groups.

Adverse effects: In this study, no reports of adverse effects by volunteers were received.

TABLE 1

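### Seventy participants do not give 90% power for 90% versus 60% at the two-sided 5% level: power is about 84–87% by normal approximation and about 78% for Fisher's exact test

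*Combined protocol and SAP*

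**What the plan says.** Under Sample size calculation (Materials and Methods), the document makes the absolute risk of tooth sensitivity the primary outcome and states that "a minimum sample size of 70 participants was required to have a 90% chance of detecting, as significant at the 2-sided 5% level", the effect being "a decrease in the primary outcome measure from 90% in the control group to 60% in the experimental group". It gives no formula, software or dropout allowance, and names no test for the calculation.

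The other inputs are stated elsewhere:

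- **Allocation** (Random sequence generation and allocation concealment): "blocked randomization (block sizes of 2 and 4) with an equal allocation ration". Seventy participants is therefore 35 per arm, and the Table 2 rows agree (33 + 2 and 28 + 7).
- **Primary analysis** (Statistical analysis): "The absolute risk of TS and its intensity were evaluated by using Fischer's exact test", at the 5% level. No side is given there.
- **Losses** (Results, Protocol adherence and dropouts): "No discontinuity in both treatment groups was found in the clinical investigation".

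**The concern.** The sentence gives everything needed to check it: two proportions, a significance level with its side, a power and a total size. No outside figure is required. A 30-point difference from 90%, tested two-sided at 5% with 90% power, normally needs about 40 per arm rather than 35, and Fisher's exact test, being conservative, needs more.

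This is the only power statement in the document, it concerns the primary outcome, and the trial reported no significant difference on that outcome. The Results rest that conclusion on the p-value and the confidence interval, not on the 90% figure. A reader may still use the stated power to judge how strongly a null result argues against a 30-point reduction, and would then understate the risk of a false negative.

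**Working it through.** **Inputs.** p1 = 0.90, p2 = 0.60, difference 0.30; two-sided α = 0.05 (z = 1.960); power 0.90 (z = 1.2816); 35 per arm. Sum of variances: 0.90 × 0.10 + 0.60 × 0.40 = 0.09 + 0.24 = 0.33. Mean proportion 0.75, so the pooled term is 2 × 0.75 × 0.25 = 0.375.

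**Step 1. Trying to reproduce 70 at 90% power (n per arm, two-sided)**

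- Unpooled: (1.960 + 1.2816)² × 0.33 / 0.30² = 38.5, so 39 per arm, 78 in total.
- Arcsine: h = 2·arcsin√0.90 − 2·arcsin√0.60 = 0.726; 2 × (1.960 + 1.2816)² / h² = 39.9, so 40 per arm, 80 in total.
- Pooled: (1.960 × √0.375 + 1.2816 × √0.33)² / 0.30² = 41.7, so 42 per arm, 84 in total.
- Pooled with continuity correction: 49 per arm, 98 in total.

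None gives 70.

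**Step 2. Power at 35 per arm (two-sided 5%, normal approximation)**

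The standard error under the alternative is √(0.33/35) = 0.0971; the pooled one is √(0.375/35) = 0.1035.

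- Unpooled: Φ(0.30/0.0971 − 1.960) = Φ(1.130) = 87.1%.
- Arcsine: Φ(0.726 × √17.5 − 1.960) = Φ(1.077) = 85.9%.
- Pooled: Φ((0.30 − 1.960 × 0.1035)/0.0971) = Φ(1.000) = 84.1%.
- Pooled with continuity correction: Φ((0.30 − 1/35 − 1.960 × 0.1035)/0.0971) = 76.0%.

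**Step 3. Exact power at 35 per arm**

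This sums the binomial probabilities at 0.90 and 0.60 over all 36 × 36 possible tables with p ≤ 0.05.

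| Test | Power at 35 per arm |
|---|---|
| Pearson chi-square, two-sided | 85.2% |
| Fisher's exact, two-sided | 78.5% |
| Fisher's exact, one-sided 5% | 86.7% |

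Two-sided Fisher has 84.0% power at 39 per arm, 87.4% at 42 and 89.8% at 46. It first reaches 90% at 47 per arm (90.6%), which is 94 participants.

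**Step 4. Size of the shortfall**

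- Participants: 78 − 70 = 8 to 84 − 70 = 14 by uncorrected normal approximation; 94 − 70 = 24 for Fisher.
- Type II error: 100 − 87.1 = 12.9% to 100 − 84.1 = 15.9% by uncorrected normal approximation; 100 − 78.5 = 21.5% for Fisher; stated, 10%.
- What 35 per arm detects with 90% power is a fall from 90% to about 57–58% (normal approximation) or about 54% (Fisher).

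**Step 5. Where 70 may come from**

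With a one-sided 5% level (z = 1.645) the pooled formula gives 33.8, so 34 per arm and 68 in total. Power at 35 per arm is then Φ((0.30 − 1.645 × 0.1035)/0.0971) = 90.9%. Seventy is also what the arcsine formula gives for 85% power two-sided. Either source is an inference, since the document shows no formula.

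Table 2 is consistent with one-sided working. For 33/35 versus 28/35, one-sided Fisher gives p = 0.0753 and two-sided Fisher gives 0.151; the reported value is 0.075. Uncorrected chi-square gives 0.0742, which rounds to 0.074.

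**The case against.** The strongest reply is that 70 and 90% do fit together under a standard formula if the test is one-sided: 68 participants, or 90.9% power at 35 per arm. The wrong item may then be the stated side rather than the power. This stands as an explanation, and the reported p-value lends it some support. It does not make the sentence correct, because the sentence specifies a two-sided level. Nor does it hold for the named test, since one-sided Fisher reaches only 86.7%.

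A second reply is that planning by normal approximation and analysing with Fisher is common, so the drop to 78% mixes two issues. That is fair as a distinction: the gap within the normal approximations is 3 to 6 points, and the rest comes from the choice of test. But every two-sided approximation tried misses 90% without any appeal to Fisher, and the 84–87% range leaves out the continuity-corrected 76.0%, which would widen the gap.

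Third, the source literature is described as reporting approximately 90%, and the shortfall is sensitive to that rate. The unpooled formula needs 35.2 per arm at 91% and 32.2 at 92%. The calculation itself, however, starts from 90%.

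Finally, the trial is complete, no participant was lost, and no reported result depends on the power figure. That limits the consequence and argues for a small remedy. It does not make the figure right.

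**Conclusion.** The concern holds. As written, the power statement for the primary outcome is wrong: at the stated rates and two-sided 5% level, 35 per arm gives 84–87% power by uncorrected normal approximation and 78.5% with two-sided Fisher's exact test. By even the most lenient of these methods the sample is 8 participants short. Under the named test it is 24 short, and the risk of missing the planned effect is more than double the stated 10%.

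This rests on equal arms of 35, which Table 2 confirms, and on the 90% and 60% rates as stated. The Fisher figures also take the primary test as two-sided; the Statistical analysis section gives no side, so that is read from the level in the sample size sentence. The normal-approximation shortfall does not depend on the choice of Fisher. No dropout allowance could explain the gap, because an allowance would raise the number and not lower it.

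**What to change.** Replace the power sentence with wording such as: *With 70 participants (35 per arm), power to detect 90% versus 60% at the two-sided 5% level is about 78% with Fisher's exact test (84–87% by normal approximation).* If the sponsor can recover the formula, test and side that produced 70, naming them next to the corrected figure would show how the discrepancy arose.

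The cost is one sentence and a less favourable power figure. No further patients are needed, and neither the primary test nor any estimate changes.
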